### **Secondary Endpoints**

For the secondary outcome measures, when normality assumption holds, we will test the association between outcomes and the arms of the study using linear mixed model; otherwise generalized linear mixed effects models will be used with the appropriate distribution function. Random study site effect will be tested; if significant, it will be included in the modeling; if insignificant, the models will be simplified to linear or generalized linear models. Appropriate transformations may be used to satisfy the normality assumptions of the model, if needed. Baseline corticosteroid/immunosuppressive therapy use will be included as a covariate in

the models. To evaluate factors associated with drug responsiveness, we will use models as described above but restrict the analyses to those in the medication arm of the study.

For the primary and secondary outcome measures, sensitivity analyses may be done by including the following covariates in the models described above: sex, age group, baseline eosinophil counts, missing last injection before EGD, and baseline disease severity. Given the sample size, covariates will be tested individually in the models.

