13.5.4. Analyses of Secondary and Other Endpoints

For the secondary and exploratory outcome measures related to differences between the arms of the study, generalized linear mixed effects models will be used with the appropriate distribution function and link function (e.g. binomial distribution and logit link for binary outcomes, normal distribution and identity link for normally distributed continuous outcomes). Appropriate transformations may be used to satisfy the normality assumptions of the model, if needed. Baseline corticosteroid/immunosuppressive therapy use will be included as a covariate in the models. Study site will be included as a random effect in the models. To evaluate factors associated with drug responsiveness, we will use generalized linear mixed models as described above but restrict the analyses to those in the medication arm of the study. Statistical testing will be performed at the two-sided 5% level of significance.

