## Sample Size Considerations

As we recognize that not all participants may complete the study, a dropout rate of 10% is assumed for all sample size calculations provided below.

It is assumed that the true mean percent reduction from baseline in mean gastric eosinophil counts when treated with dupilumab will be at least 50%. This is a conservative estimate based on the efficacy of dupilumab in EoE patients; dupilumab reduced the mean (least square) peak esophageal eosinophil count by -94/HPF (9.5 standard error; n=23) and -7.4 (9.6 standard error; n=24) in the placebo group in a recent study of EoE13. At Week 12, dupilumab versus placebo significantly reduced peak eosinophil counts from baseline (-92.9% vs +14.2%; P<0.0001). It is also assumed that the true mean percent reduction from baseline in mean eosinophil counts for the placebo group will be at most 25% and we expect it to be much less as the placebo effect in EoE was 14% increase in eosinophil levels as noted above. Assuming a standard deviation of 25 percentage units, a sample size of 20 participants per treatment group will provide at least 80% power to detect a true absolute difference in percent reduction from baseline in mean eosinophil counts of 23% at alpha = 0.05. If we assume that the dropouts from the dupilumab arm have a mean reduction in eosinophil counts similar to those on placebo (25%) then we would expect 48% decline in eosinophil count among those in the dupilumab arm, thus we are sufficiently powered even with dropouts. A sample size of 20 per treatment group will also provide at least 80% power to detect a difference in the proportions of participants with induction of disease remission of 42 percentile points (e.g. 62% vs. 20%) at the two-sided 5% level of significance. Notably, if 2 individuals in the dupilumab arm drop out then the effective disease remission rate would be 67% among those completing the study in order to obtain a 62% overall remission rate for the dupilumab arm.

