### Hierarchical Testing structure

We will employ a hierarchical testing strategy to minimize the impact of multiple testing for the key secondary outcomes from the double blind. Thus, p-values will be reported only when prior outcomes had reached

significance ( $p \leq 0.05$ ). Once an outcome fails to reach significance the confidence intervals of the estimates will be reported.

|                      | End Points   | Order |
|----------------------|--|-------|
| Primary       | Relative change in mean of the peak gastric count                          | 1     |
| Key Secondary | Absolute change in EoG-HSS   | 2     |
|                      | Absolute change in mean of the peak gastric count                          | 3     |
|                      | Absolute change in EoG-REFS (total score – sum of antrum, body, fundus)    | 4     |
|                      | Absolute change in the total EG-SQ eDiary score                            | 5     |
|                      | Proportion achieving response (< 30 eos/hpf in all 5 hpfs)                 | 6     |
|                      | Absolute change in PGI-S score   | 7     |
|                      | PGI-C score  | 8     |
|                      | Absolute change in proportion of days of any (1 or more) symptom in EoG-SQ | 9     |

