## Statistical Analyses

### *General Principles*

Statistical analyses will be reported using summary tables, figures, and data listings. Continuous variables will be summarized with counts, means, standard deviations, medians, confidence intervals, minimums, and/or maximums. Categorical variables will be summarized by counts and by percentage of patients. Formal inferential statistical analyses techniques will be discussed in subsequent sections of this SAP. Statistical testing will be performed at the two-sided 5% level of significance.

All analyses will be performed using SAS Version 9.4 or higher on a PC platform. Table, listings, and figures will be presented in Word format. Upon completion, all SAS programs will be validated by an independent programmer. In addition, all program output will undergo a senior level statistical review. The validation process will be used to confirm that statistically valid methods have been implemented and that all data manipulations and calculations are accurate. Checks will be made to ensure accuracy, consistency with this plan, consistency within tables, and consistency between tables and corresponding data listings. Upon completion of validation and quality review procedures, all documentation will be collected and filed by the project statistician or designee.

Prior to statistical analysis, quality and distribution of the data will be examined. All individuals completing study visit 1 will be included in the analysis of the primary outcome including participants receiving steroids within the last 30 days before endoscopy. The patterns of data missingness will be evaluated by reviewing patient drop out reasons and comparing baseline patient characteristics. Missing outcome data will then be imputed using multiple imputation. Factors to be considered in the multiple imputation are the prior eosinophil counts, participant clinical characteristics and longitudinal secondary outcomes. If differences occur between the results of the ITT and PP analyses, we will explore the data to understand the pattern of missingness, using tipping point analysis to understand the impact of the missing data on inference, and consider additional imputation.

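### Six key secondary change-from-baseline endpoints are modelled without their own baseline value: an avoidable loss of precision, whose size depends on a baseline spread the documents do not give

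*SAP*

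**What the plan says.** The SAP (Efficacy Analyses, Secondary Endpoints) compares the arms by a linear mixed model, or a generalized one if normality fails. "Baseline corticosteroid/immunosuppressive therapy use will be included as a covariate". A random site effect is tested and dropped if not significant, and transformations are allowed. Protocol 13.5.4 agrees on the covariate ("Baseline corticosteroid/immunosuppressive therapy use will be included as a covariate in the models") and includes site as a random effect.

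Baseline eosinophil count and a baseline disease severity that is not defined appear only among optional sensitivity covariates, entered singly (SAP, same section; Protocol 13.5.3). The baselines of EoG-HSS, EoG-REFS, EG-SQ and PGI-S are not named.

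The SAP's Hierarchical Testing structure ranks nine endpoints. Ranks 2, 3, 4, 5, 7 and 9 are absolute changes, and rank 3 is "Absolute change in mean of the peak gastric count". After the first non-significant result, confidence intervals replace p-values. The level is set under General Principles: "Statistical testing will be performed at the two-sided 5% level of significance".

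**The concern.** If a treatment removes a share of the eosinophils, the absolute fall is larger in patients who start higher. Without baseline in the model, that spread stays in the residual, and a chance baseline imbalance at 20 per arm adds noise to the estimate. Entry requires at least 30 eos/hpf in at least five fields (Protocol 4.2, criterion 4) and sets no upper limit on the gastric count, so the spread could be wide.

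The order of testing raises the stakes. A miss at rank 3 removes p-values for endoscopy, symptoms, response and both patient global ratings. The optional sensitivity analyses do not help, because the SAP gives them no place in the sequence.

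**Working it through.** **Inputs from the SAP, Sample Size Considerations.** "a sample size of 20 participants per treatment group will provide at least 80% power"; "Assuming a standard deviation of 25 percentage units"; a detectable difference in "percent reduction from baseline in mean eosinophil counts of 23% at alpha = 0.05". The mean dupilumab reduction "when treated with dupilumab will be at least 50" per cent and the placebo reduction is at most 25 per cent.

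**Assumed.** Baseline mean count 100, and baseline CV from 0.2 to 1.0. The documents give no mean or spread for gastric counts and no correlation between baseline and week 12.

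**1. The plan's own figure (primary endpoint).** SE = 25 × √(2/20) = 7.91; 23/7.91 = 2.91; Φ(2.91 − 1.96) = 82.9%. The noncentral t gives 80.9%. The stated 80% reproduces. The documents state no power for rank 3.

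**2. Closed form for rank 3.** Let absolute change = B × R, with baseline B (mean 100, CV c) and an independent relative change R (mean r, SD 0.25).
- Variance of change in one arm, no baseline in the model: 625(1 + c²) + 10,000c²r².
- With baseline and a common slope of −0.375 (the average of −0.50 and −0.25): 625(1 + c²) + 10,000c² × 0.125².
- Mean difference: 25.

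At c = 0.5:
- Without baseline, summing arms: 1,562.5 + 781.25 = 2,343.75; divided by 20 = 117.2; SE 10.83; 25/10.83 = 2.31; power Φ(0.35) = 64%.
- With baseline: 1,562.5 + 78.1 = 1,640.6; divided by 20 = 82.0; SE 9.06; 25/9.06 = 2.76; power Φ(0.80) = 79%.

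At c = 1.0 the variance sums are 5,625 and 2,812.5, giving 32% and 56%. The gap (24 points) agrees with the simulation below. The levels are lower because the normal approximation handles a skewed baseline poorly.

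**3. Simulation.** Baseline is a lognormal shifted to start at 30, with mean 100. There are 10,000 trials per row, 20 per arm, and steroid use in both models.

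| Baseline CV | Without baseline | With baseline | Gain (points) |
|---|---|---|---|
| 0.2 | 82% | 84% | 2 |
| 0.3 | 77% | 82% | 5 |
| 0.4 | 71% | 80% | 10 |
| 0.5 | 64% | 78% | 14 |
| 0.6 | 58% | 76% | 17 |
| 0.75 | 51% | 72% | 21 |
| 1.0 | 42% | 67% | 25 |

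A lognormal truncated at 30 (4,000 trials; nominal CV 0.5, 0.7, 1.0) gives 64%, 54%, 43% without baseline and 78%, 74%, 69% with it. Repeat runs put the gain at CV 1.0 between 23 and 26 points. With 18 per arm, or with 48% versus 25%, the gains in the shifted-lognormal runs are similar (2 to 24 points).

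**4. Other effects.** Truncated lognormal, CV 0.5, 0.7, 1.0:
- 50% versus 10%: 98%, 93%, 86% without baseline; 99%, 98%, 96% with it.
- 50% versus 0%: 100%, 99%, 97% without baseline; 100%, 100%, 99% with it.

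Shifted lognormal, CV 0.4 to 0.75:
- 60% versus 10%: gain 0 to 3 points.
- 50% versus 25% with SD 40: gain 3 to 6 points.

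**5. Reaching rank 4.** The chance that the primary and rank 3 are both significant (rank 2 not modelled, 50% versus 25%) is 69% without baseline and 78% with it at CV 0.4. At CV 0.75 it is 50% and 71%.

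**6. The other five change scores.** With equal variance σ² at baseline and follow-up and correlation ρ, the variance is 2σ²(1 − ρ) for raw change and σ²(1 − ρ²) after adjustment. The ratio is (1 + ρ)/2. At ρ = 0.5 this is 0.75, equivalent to 1/0.75 = 1.33 times the patients. If raw change has 80% power, adjustment gives 95% at ρ = 0.2, 90% at 0.5 and 84% at 0.8. Equal variances and every ρ here are assumptions.

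**The case against.** - **The effect is the plan's least favourable.** The SAP calls 50% a minimum for dupilumab and 25% a maximum for placebo, and expects placebo to do much less. With a placebo reduction of 10% or 0%, little power is lost. This stands, and it is why the size must be a range.
- **The simulated analysis is not exactly the planned one.** The figures use normal-theory models on raw change, whereas the SAP allows transformations or another distribution. As an illustration, a rank test (not named in that SAP section) at 50% versus 25% gives 71%, 65%, 60% at CV 0.5, 0.7, 1.0, against 65%, 53%, 43% for raw change and 79%, 74%, 68% with baseline. It recovers 6 of 14, 12 of 21 and 17 of 25 points. This stands in part: the option may narrow the gap, but it is discretionary and does not put baseline in the model.
- **The planned comparison is valid.** It is: null simulations rejected about 4 to 5% of the time with or without baseline. A reader might infer bias from chance imbalance, but randomisation rules that out and the standard error already reflects the imbalance.
- **Baseline is already covered.** Baseline count is a listed sensitivity covariate, and baseline scores are to be compared by arm (SAP, Description of Demographic and Baseline Characteristics). These provisions are partial: the covariate analyses are optional, four of the own baselines are not named, and none affects the testing sequence.

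**Conclusion.** The omission is real and adjustment would improve precision at almost no cost. At the planning effect, rank 3 loses about 2 points of power at baseline CV 0.2, 14 at 0.5, 20 at 0.7 and 23 to 26 at 1.0. It loses about 0 to 10 points if the placebo reduction is 10% or 0%. All of this rests on an assumed baseline mean of 100, a relative change independent of baseline, and normal-theory analysis of raw change.

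A reader might infer a flat loss of about 20 points. The documents do not support that, because it needs a CV near 0.7 together with the least favourable effect. A reader might also infer that the main model should now be replaced. The SAP Revision History (version 2.4) and Statistical Analysis Changes From the Protocol report close agreement between imputed and complete-case results and a dropout in the placebo arm. Results had therefore been seen, and changing the model behind the sequential p-values would be a results-aware change. The point concerns the six change scores only. Ranks 6 (response) and 8 (PGI-C) are not changes from baseline, and no gain has been shown from adding a baseline to either.

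**What to change.** In principle, every change-from-baseline model in the SAP's Secondary Endpoints and Exploratory Endpoints sections should include the endpoint's own baseline as a fixed covariate.

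At this stage:
- Keep the present model for the p-values in the fixed sequence.
- Report own-baseline-adjusted estimates and 95% confidence intervals for all six change scores (ranks 2, 3, 4, 5, 7, 9) as one complete supplementary set. Reporting all six prevents selective use.
- Label the set post hoc and exploratory, as the SAP Introduction requires for analyses not defined prospectively.
- Leave the PGI-C model as it is.

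The cost is a short SAP addition, one supplementary table and one degree of freedom per model. The baseline measures are already collected, so no new data are needed.

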8.2.1. Screening Period (-8 to 0 weeks)

During the screening period (-8 to 0), informed consent will be obtained, and inclusion/exclusion criteria will be reviewed.

The following activities will occur:

- Consent
- Review eligibility criteria
- Demographics, Medical history
- Review of AE and concomitant medication
- Physical Examination
- Vital signs, and height, weight
- Blood draw (laboratory, biomarker (includes total IgE))
- Serum Pregnancy
- Diet assessment
- Questionnaires
- Screening endoscopy (biopsies, endoscopic features)
- ACT™ (Asthma Control Test) questionnaire

When the results of all screening activities are available, the PI will make a determination of study eligibility.

If it has been confirmed that a participant does not meet inclusion and/or exclusion criteria, the participant will be considered a screen failure. Screen failed participants may be re-screened up to two additional times at the discretion of the site investigator. If the screen failure was due to a concomitant medication that can be discontinued prior to rescreening, re-screening may be appropriate. Rescreening with repeat EGD (for failed eligibility scope) may occur at time points consistent with clinical care (every 2-3 months). The window during which a patient may rescreen for other entry criteria is the length of screening window

(8 weeks). Other potential reasons for rescreening (i.e. reasons unrelated to the inclusion/exclusion criteria) must be approved by the study principal investigator prior to rescreening the participant.

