8.3. Baseline/Initiating Treatment

Visit 1 (Week 0)

- Review inclusion/exclusion criteria for final determination of study eligibility
- Urine pregnancy test
- Randomization
- Vital signs, and weight
- Physical Examination
- Review of AE and concomitant medication
- Blood draw (laboratory, genomic)
- Questionnaires
- Diet assessment
- Training of participant and/or caregiver on administration of injection
- Administer study medication (by clinic staff, patient, or caregiver)
- Post-treatment monitoring for 30 minutes

Participants or their caregivers are expected to complete supervised study product administration at a minimum of one clinic visit before the participant/caregiver administers injections at home.

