We will evaluate the absolute change in PROs during the double blind period and the OLE treatment period. Exploratory PROs will include the Severity of Dyspepsia Assessment tool as well as a QOL (SF-12, PROMIS 29 and PROMIS 25) scores. We will also utilize clinician global impression of severity and clinician global impression of change. The SODA will be collected at the screening visits and all study visits (visits 1, 2, 3, 4 & 5) during the double-blind and OLE treatment periods.

The induction of disease remission defined by the percentage of participants who achieve histological remission in the stomach as defined by peak eosinophil counts less than 30/hpf in 1, 2, 3 and 4 of the 5 hpf identified for the primary endpoint. Comparison between drug vs placebo at week 12 will be the measurement endpoint. This information will be gathered by collecting biopsies at the 12-week visit, which are converted into slides, and then evaluated on Histology Scoring Sheets by the central pathology core.

The absolute change in histologic score from pre- to post-treatment with dupilumab or placebo as measured by the EG Biopsy Evaluation Form. For those participants with esophageal involvement or duodenal involvement, we will assess absolute changes in histology using the EoE-HSS and ED Biopsy Evaluation Form respectively. The biopsy evaluation forms will be gathered at the screening visit and the visit 5 end of treatment visit at the end of the double-blind treatment period.

The absolute and relative change in blood biomarkers (primarily cytokine levels) and tissue biomarkers as well as gastric transcripts before and after treatment. The blood biomarkers will be evaluated at the screening visit and visits 1 and 5 of the double-blind treatment period.

The absolute and relative change in blood eosinophil count, hemoglobin, hematocrit, protein levels, IgE, iron storage panel (iron, ferritin, total iron-binding capacity) before and after treatment with dupilumab or placebo (total protein and albumin levels). The CBC with differential will be gathered at the screening visit and all visits (visits 1, 2, 3, 4 & 5) during the double-blind treatment period. The serum chemistry will be evaluated at the screening visit and visits 2 and 5 of the double-blind treatment period.

The association of blood and tissue biomarkers and transcripts with drug responsiveness.

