### *Exploratory Endpoints*

#### *Double-blind*

- 1) Absolute change in SODA, SF-12, PROMIS 29, PROMIS 25, and CGI-S scores
- 2) CGI-C score at 12 weeks
- 3) Absolute change in proportion of days with each individual symptom and multiple symptoms measured by the EoG-SQ eDiary.
- 4) Absolute change in each individual EoG-SQ eDiary symptom score
- 5) Induction of disease remission (percentage who achieve histological remission in the stomach as defined by peak eosinophil counts less than 30/hpf in 1, 2, 3 and 4 of the 5 hpfs identified for the primary endpoint).
- 6) For participants with esophageal involvement and/or duodenal eosinophilia involvement, absolute change in EoE HSS and EoD HSS respectively.
- 7) Absolute and relative change in blood and tissue biomarkers and gastric transcripts
- 8) Absolute and relative change in blood eosinophil count, hemoglobin, hematocrit, total protein levels, albumin, IgE, iron storage panel (iron, ferritin, total iron-binding capacity)
- 9) The association of blood and tissue biomarkers and transcripts with drug responsiveness.
- 10) Absolute changes in esophageal and duodenal peak eosinophil levels.
- 11) Absolute changes in EoE-EREFs and EoD-EREFs in participants with esophageal and/or duodenal involvement, respectively.

For double-blind endpoints above, a comparison between drug vs placebo at 12 weeks will be made.

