## ***Efficacy Analyses***

### **Primary Endpoint**

The primary outcome measure will be the relative change in the mean of the eosinophil counts from the 5 worst microscopic fields in the gastric antrum and/or body. Relative change is defined as (week 12 – baseline)/baseline. Regression analyses will be performed with the primary outcome measure as the dependent variable and treatment group as the independent variable. Appropriate transformations, such as a log-transformation, may be used to satisfy the distributional assumptions prior to model fitting. If there are continued concerns about data distributions, equivalent nonparametric tests will be employed. To ensure that immunosuppression (e.g. corticosteroid, swallowed glucocorticosteroids for EoG (Entocort), or immunosuppressive agents) use does not influence results, we will also perform regression analyses with corticosteroid/immunosuppression therapy as a covariate (including considering binary (y/n), and dose (none, low, high)).

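### Factors for drug responsiveness are modelled in the dupilumab arm only, which cannot separate response to the drug from prognosis; the week-12 placebo slope should be shown beside it

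*SAP*

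**What the plan says.** The SAP lists among its double-blind exploratory endpoints (item 9): "The association of blood and tissue biomarkers and transcripts with drug responsiveness". The method is in SAP, Efficacy Analyses, Secondary Endpoints: "To evaluate factors associated with drug responsiveness, we will use models as described above but restrict the analyses to those in the medication arm". Protocol 13.5.4 agrees: "we will use generalized linear mixed models as described above but restrict the analyses to those in the medication arm of the study". The models referred to are those for the secondary outcomes (in the protocol, also the exploratory ones). No single outcome is named as the measure of responsiveness, and no sample is named as the source of the marker.

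The double-blind exploratory list closes with a general sentence: "For double-blind endpoints above, a comparison between drug vs placebo at 12 weeks will be made". It makes no exception for item 9 and gives no method for it.

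On marker timing, Protocol 13.2 says: "The blood biomarkers will be evaluated at the screening visit and visits 1 and 5 of the double-blind treatment period". The screening list (Protocol 8.2.1) includes a biomarker draw. The Visit 1 list (Protocol 8.3) gives only "Blood draw (laboratory, genomic", and the Visit 2 list (Protocol 8.4.1) names a biomarker draw. Table A, as far as its damaged layout can be read, puts the second draw at Visit 1. Biopsies are taken from all participants (Protocol 9.1). The same association appears for the open-label extension as item 14, where everyone receives dupilumab.

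**The concern.** A regression of outcome on marker among treated participants mixes two things: how the marker relates to change whatever the treatment, and how it modifies the effect of the drug. Only a comparison with untreated participants separates them. The plan itself allows a mean reduction of up to 25% on placebo (SAP, Sample Size Considerations), so change without the drug is not ruled out.

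The name of the endpoint invites a drug-specific reading. A purely prognostic marker could then be reported as a marker of response to dupilumab, although the trial holds randomised week-12 placebo data that could check it. Timing also matters. A marker measured before the first dose supports a clean test of effect modification. A marker measured on treatment may itself be changed by the drug.

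**Working it through.** **The plan's own figure.** The documents give no figure for this analysis. Their sample-size statement reproduces: n = 2 × (1.960 + 0.842)² × (25/23)² = 18.6, so 19 per arm. At 20 per arm the t-test power is 80.9%, against the stated minimum of 80%.

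**Inputs.** 20 per arm, SD 25 points, mean changes of -50% and -25% (SAP, Sample Size Considerations); two-sided 5% (SAP, General Principles); one placebo dropout (SAP, Statistical Analysis Changes From the Protocol), hence 20 vs 19. Marker-outcome correlations, the 0% placebo change and the log-scale SDs are assumptions.

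**Prognostic marker, same correlation r in both arms.** Approximate chance that the dupilumab-arm slope is significant with n = 20: Φ(atanh(r) × √17 - 1.96).
- r = 0.3: 0.3095 × 4.123 = 1.276; Φ(-0.684) = 25%.
- r = 0.5: 0.5493 × 4.123 = 2.265; Φ(0.305) = 62%.

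Simulation gives 25% and 63-64%. The marker-by-treatment interaction in the same setting is significant in about 5%.

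**True modifier, r in the dupilumab arm and no slope on placebo.** At r = 0.5 with equal outcome variance, the SE of the slope difference is about √(0.75/19 + 1/18) = 0.308. Then 0.5/0.308 = 1.62 and Φ(1.62 - 2.03) = 34%. Simulation with baseline count and steroid use in the model gives 14% at r = 0.3 and 32-36% at r = 0.5, depending on the variance assumption. The 95% CI half-width for the slope difference, in the prognostic setting, is about 0.61-0.69 outcome SD per marker SD.

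**Scale.** Simulated rate of a significant interaction, 20 vs 19, for a marker that is only prognostic (log SD 0.3 or 0.5; for the log ratio, near-zero counts floored at 1% or 5% of baseline):

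| Marker acts on | Analysed as | -50% vs -25%, r = 0.3 / 0.5 | -50% vs 0%, r = 0.3 / 0.5 |
|---|---|---|---|
| counts, proportionally | relative change | about 7% / 11% | about 9-10% / 17-19% |
| counts, proportionally | log ratio | about 5% / 5% | about 5% / 5% |
| relative change, additively | relative change | about 5% / 5% | about 5% / 5% |
| relative change, additively | log ratio | about 7-8% / 12-14% | about 10% / 20-21% |

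Each scale holds the 5% level when it matches the way the marker acts, and exceeds it when it does not.

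**The case against.** The strongest case against is that the plan does not make the error. It speaks of association and of factors associated with responsiveness; it never claims effect modification. The endpoint is exploratory and outside the hierarchical testing structure, and one interpretive sentence would remove most of the risk. The interaction has low power. Results had already been compared when SAP version 2.4 was written, so nothing added now is prespecified. All of this stands and limits the size of the point, but it gives no reason to leave the randomised control arm unused.

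A reader might infer more than the documents support:
- *That the planned analysis has a 25-64% false-positive rate.* It does not. Read as association on dupilumab, those rates are power.
- *That the log ratio makes the interaction safe.* The table shows it only moves the dependence on scale. The SAP permits a log transformation ("Appropriate transformations, such as a log-transformation, may be used to satisfy the distributional assumptions prior to model fitting"), but nothing in either document says which scale a marker acts on, and the trial is powered on percent change.
- *That the closing sentence of the exploratory list already brings placebo into item 9, or seriously contradicts the rule.* It is one blanket sentence against a specific rule: a matter of wording.
- *That the differing visit lists leave no clean baseline marker.* The screening sample is pre-dose on any reading, and Table A appears to agree with Protocol 13.2 on Visit 1.

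**Conclusion.** The point holds as an improvement to one exploratory endpoint. Restriction to the dupilumab arm is explicit in both documents, and the slope it yields cannot by itself be called specific to the drug. With about 20 treated participants, an equally prognostic marker would reach significance in roughly a quarter of trials at r = 0.3 and nearly two thirds at r = 0.5, against about 5% for an interaction fitted on the right scale. The correlations are assumed, since the documents give none. The comparison with placebo is informative but imprecise. It can cast doubt on a drug-specific reading, but a non-significant interaction does not exclude a response marker, and a significant one may reflect the choice of scale. Primary and key secondary results do not change.

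**What to change.** In SAP, Efficacy Analyses, Secondary Endpoints:
- For markers measured before the first dose (screening blood and biopsy), keep the dupilumab-arm slope, add the week-12 placebo-arm slope, and report the marker-by-treatment difference in slopes with its 95% CI. Label it hypothesis-generating and, under the rule in the SAP Introduction, post hoc and exploratory.
- State the outcome used and keep the scale of the corresponding planned analysis. For eosinophil change, show both relative change and the log ratio as a sensitivity check, with a stated rule for zero counts.
- Describe results for markers measured after dosing starts, and for item 14 of the open-label extension, as association with change on dupilumab.

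In the double-blind exploratory list, refer item 9 to this section so that the closing sentence does not appear to govern it.

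The cost is SAP wording and one further model per marker on about 39 people. With baseline count and steroid use included, that is six coefficients instead of three on 20 people. No new visits or samples are needed, though stored placebo samples may still have to be assayed. The main drawback is the low power shown above, which is why the estimate and its interval should be reported rather than a pass-or-fail test.
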